6.3 SUBJECT SETS ANALYSED

Subject sets will be used as defined in the **Section 7.3 of the CTP**:

Part A:

- *Treated set - part A (TS-A): The treated set includes all subjects who were randomized and treated with at least one dose of study drug. The treated set will be used for safety analyses.*
- *Pharmacokinetic parameter analysis set - part A (PKS-A): This set includes all subjects in the treated set - part A (TS-A) who provide at least one PK endpoint that was defined as primary or secondary and was not excluded due to a protocol violation relevant to the evaluation of PK or due to PK non-evaluability (as specified in the following subsection 'Pharmacokinetics'). Thus, a subject will be included in the PKS, even if he/she contributes only one PK parameter value for one period to the*

statistical assessment. Descriptive and model based analyses of PK parameters will be based on the PKS.

Part B (stage I and II):

- *Treated set - part B (TS-B): The treated set includes all subjects who were randomized and treated with at least one dose of study drug. The treated set will be used for safety analyses.*
- *Pharmacokinetic parameter analysis set - part B (PKS-B): This set includes all subjects in the treated set - part B (TS-B) who provide at least one PK endpoint that was defined as primary or secondary and was not excluded due to a protocol violation relevant to the evaluation of PK or due to PK non-evaluability (as specified in the following subsection 'Pharmacokinetics'). Thus, a subject will be included in the PKS, even if he/she contributes only one PK parameter value for one period to the statistical assessment. Descriptive and model based analyses of PK parameters will be based on the PKS.*

[figure not shown]
Table 6.3: 1 Subject sets analysed

Part A:

Class of endpoint	Subject set	
	TS-A	PKS-A
Disposition	X	
IPDs	X	
Primary endpoints		X
Secondary endpoints		X
Further PK endpoints		X
Safety parameters	X	
Demographic/baseline conditions	X	
Exposure	X	

Part B:

Class of endpoint	Subject set	
	TS-B	PKS-B
Disposition	X	
IPDs	X	
Primary endpoints		X
Secondary endpoints		X
Further PK endpoints		X
Safety parameters	X	
Demographic/baseline conditions	X	
Exposure	X	

6.5 POOLING OF CENTRES

This section is not applicable because the trial is performed in only one centre.

6.6 HANDLING OF MISSING DATA AND OUTLIERS

Data of screened subjects who were withdrawn from the trial prior to first administration of any study drug will not be reported in the CTR.

Data of subjects who failed to complete all periods of the study (dropouts or withdrawals) will be reported in the CTR as far as their data are available. All withdrawals will be documented and the reason for withdrawal reported in the CTR.

CTP Section 7.5.1: *It is not planned to impute missing values for safety parameters.*

One exception where imputation might be necessary for safety evaluation are AE dates. Missing or incomplete AE dates are imputed according to BI standards (3).

Missing data and outliers of PK data are handled according to BI standards (4) and (5).

CTP Section 7.5.2: *PK parameters that cannot be reasonably calculated based on the available drug concentration-time data will not be imputed.*

6.7 BASELINE, TIME WINDOWS AND CALCULATED VISITS

For all parameters, the last non-missing value determined prior to first dosing of the trial medication of the respective treatment period will be defined as baseline.

For plasma concentrations:

Individual endogenous TPA will be determined for each period as a mean of two measurements at baseline. Individual baseline levels will then be subtracted from all concentration measurements in that treatment period. In case the resulting concentration value is negative, it will be set to zero.

Time windows are defined in Section 6.1 of the CTP. Adherence to time windows will be checked at the RPM.

7. PLANNED ANALYSIS

The analyses for endpoint apply for both study parts Part A and Part B. However, since the data of Part A could not be used for a formal statistical assessment all analyses in Part A are only considered to be descriptive.

The data from Part A will be analyses separately and will not contribute to the bioequivalence assessment.

The format of the listings and tables will follow the BI guideline "Standards for Reporting of clinical trials and project summaries" (6).

The individual values of all subjects will be listed. Listings will be sorted by treatment group/sequence, subject number and visit (if visit is applicable in the respective listing). AE listings will be sorted by assigned treatment (see [Section 7.8.1](#) below for details). The listings will be contained in Appendix 16.2 (SDL) of the CTR.

The following standard descriptive statistical parameters will be displayed in summary tables of continuous variables:

N	number of non-missing observations
Mean	arithmetic mean
SD	standard deviation
Min	minimum
Median	median
Max	maximum

For plasma concentrations as well as for all PK parameters the following descriptive statistics will additionally be calculated:

CV	arithmetic coefficient of variation
gMean	geometric mean
gCV	geometric coefficient of variation

For PK parameters the following descriptive statistics will additionally be calculated:

P10	10 th percentile
Q1	1 st quartile
Q3	3 rd quartile
P90	90 th percentile

The data format for descriptive statistics of plasma concentrations will be identical with the data format of the respective concentrations. The descriptive statistics of PK parameters will be calculated using the individual values with the number of decimal places as provided by the evaluation program. Then the individual values as well as the descriptive statistics will be reported with three significant digits in the CTR.

Tabulations of frequencies for categorical data will include all possible categories and will display the number of observations in a category as well as the percentage (%) relative to the

respective treatment group. Percentages will be rounded to one decimal place. The category missing will be displayed if and only if there actually are missing values. Percentages will be based on all subjects in the respective subject set whether they have non-missing values or not.

Exclusion of PK parameters

The ADS ADPP contains column variables APEXC and APEXCO indicating inclusion/exclusion (APEXC) of a PK parameter and an analysis flag comment (APEXCO). All analyses based on the PKS are based on PK parameter values which are not flagged for exclusion, i.e. with APEXC equal to "Included" (see protocol Section 7.3).

Exclusion of plasma concentrations

The ADS ADPC (PK concentrations per time-point or per time-interval) contains column variables ACEXC or ACEXCO indicating inclusion/exclusion (ACEXC) of a concentration and an analysis flag comment (ACEXCO). Exclusion of a concentration depends on the analysis flag comment ACEXCO. For example, if ACEXCO is set to "ALL CALC", the value will be excluded for all types of analyses based on concentrations. If ACEXCO is set to "DESC STATS" the value will be excluded from descriptive evaluations per planned time point/time interval. If ACEXCO contains the addition "TIME VIOLATION" or "TIME DEVIATION", the value can be used for further analyses based on actual times. If ACEXCO is set to "HALF LIFE", the value will be excluded from half-life calculation only; the value is included for all other analyses. Excluded concentration itself will be listed in the CTR associated with an appropriate flag.

Further details are given in "Noncompartmental Pharmacokinetic / Pharmacodynamic Analyses of Clinical Studies"(4) and "Description of Analytical Transfer Files and PK/PD Data Files" (5)

7.1 DEMOGRAPHIC AND OTHER BASELINE CHARACTERISTICS

Only descriptive statistics are planned for this section of the CTR.

7.2 CONCOMITANT DISEASES AND MEDICATION

Concomitant diseases will be coded according to the most recent version of MedDRA. Concomitant medication will be coded according to the most recent version of the World Health Organisation – Drug Dictionary. Concomitant non-drug therapies will be coded according to the most recent version of MedDRA.

A medication will be considered concomitant, if it

- is ongoing at the time of first study drug administration, or
- starts within the analysis phase of the respective treatment (see [Section 6.1](#) for a definition of treatments and analysis phases).

The relevance of the concomitant therapies to the evaluation of PK will be decided no later than at the RPM.

Only descriptive statistics are planned for this section of the CTR.

7.3 TREATMENT COMPLIANCE

Treatment compliance will not be analyzed as a specific endpoint. Any deviations from complete intake will be addressed in the Report Planning Meeting (cf. [Section 6.2](#)) and described in the CTR.

7.4 PRIMARY ENDPOINT

7.4.1 Primary analysis of the primary endpoint

The statistical model used for the analysis of the primary endpoints for each stage of the trial will be an analysis of variance (ANOVA) model on the logarithmic scale as described in the CTP, section 7.3.1.

Each stage will be analyzed separately based on data from only this stage, see CTP Section 7.2.

Stage 1 analysis

After stage 1, an assessment for bioequivalence will be performed. Data of stage one will be analyzed with the statistical model described in the **CTP, section 7.3.1**.

CTP section 7.3.1 *Point estimates for the ratios of the geometric means (test/reference) for the primary endpoints (see Section 2.1) and their two-sided confidence intervals (CIs) will be provided. At stage 1, the $(1 - 2\alpha_1) * 100\%$ confidence interval for the gMean ratio will be calculated.*

The alpha spent for the first stage is fixed to 0.03585 (one-sided), see **CTP section 7.2**.

The analysis of stage 1 data will be implemented using SAS PROC MIXED:

```
PROC MIXED DATA=pks_stage1;
  CLASS subject treatment(ref==TPA-02=) sequence period;
  MODEL logkp = treatment sequence period subject / DDFM=KR;
  LSMEANS treatment / PDIFF CL ALPHA=0.0717;
  RUN;
```

Bioequivalence is concluded, if the corresponding (adjusted) confidence intervals for the comparison of the primary and secondary (same model, see CTP section 7.5.2) endpoints are within the pre-specified boundaries 80.00% to 125.00% (original scale).

1 A) If bioequivalence is shown, the trial will be closed after stage 1.

1 B) If bioequivalence is not shown for all primary and secondary endpoints after stage 1, then a decision regarding continuation of the trial will be made by the Principal Investigator, the Trial Statistician, and the Clinical Trial Lead or their respective designees.

As stated in the CTP, for all endpoints not meeting the bioequivalence criterion, the following calculations will be performed.

The power of the TOST procedure based on the first stage data will be calculated (using the planned treatment effect, the observed variability and the adjusted alpha level for stage 1). If this power is greater or equal to 0.9, the trial is recommended to stop for futility, cf. (11) Note that this futility rule is considered nonbinding.

The SSR will be based on the conditional power as described in (11), i.e. it will use the conditional error rates as well as the estimated conditional target power for the second stage. For the SSR it is planned to use the observed variability (gCV) and the observed geometric mean ratio (GMR) from the (unblinded) stage 1 data. Note that a specific power adjustment due to multiple endpoints will not be done and the sample size recalculation, if required, will be based on observed results from primary and secondary PK parameters. The calculation will be performed for each parameter and the highest sample size will be used. Note that the minimum sample size for stage 2 is set to 4, as done and recommended in (11). Moreover, for this study a maximum overall sample size of 60 will be considered.

This step may be implemented using function `interim.tsd.in` from the R package `Power2Stage`:

```
interim.tsd.in(weight = 0.8, max.comb.test = FALSE, targetpower =  
0.9,  
                 GMR1 = GMR1, CV1 = CV1, n1 = n1, ,  
                 GMR = 1.09, usePE = TRUE, max.n = 60, fCrit = "No")
```

For GMR1 and CV1 it is planned to use the observed results from stage 1, i.e. the gMean ratio and gCV as derived from the above proc mixed call. Similarly, df1 and SEM1 are the degrees of freedom and standard error of the difference of LSmeans, respectively, and are to be taken (on the log-scale) from the same proc mixed call. n1 is the number of subjects in the PKS from stage 1,

Note that the weight of 0.8 may be adjusted as described in the CTP Section 7.2.

If applicable, Stage 2 analysis

Step 2 A)

Data of stage two will be analyzed with the same statistical model described in the CTP, section 7.3.1 using in principle the same SAS dummy code as described above in [Section](#)

[7.4.1](#) of the TSAP. Note again that the input data for the proc mixed call will be PKS data from stage 2 only.

```
PROC MIXED DATA=pkstage2;
  CLASS subject treatment(ref==TPA-02=) sequence period;
  MODEL logkp = treatment sequence period subject / DDFM=KR;
  LSMEANS treatment / PDIFF CL ALPHA=2*alpha2;
RUN;
```

where α_2 is planned to be 0.03585 and may be adjusted based in accordance with the weight.

Step 2 B)

Study success will then be determined based on the standard inverse normal combination test.

CTP section 7.2 *If the study continues to the second stage, let p_{2j} denote the two p-values of the second stage, $j = 1, 2$. Note that p_{2j} are obtained using only the data from stage 2. BE is concluded (i.e. the null hypothesis is rejected) after the second stage if the combination of the p-values p_{1j} and p_{2j} ($j=1, 2$) is greater than the critical boundary c_2 for the final assessment, cf. [\(10\)](#) and [\(11\)](#):*

$$\sqrt{w}\Phi^{-1}(1 - p_{1j}) + \sqrt{1 - w}\Phi^{-1}(1 - p_{2j}) \geq c_2,$$

where $j = 1, 2$ and j again refers to the j -th hypothesis of the TOST procedure and Φ refers to the cumulative distribution function of the standard normal distribution.

Note that α_2 and the critical value c_2 , will possibly adapted according the user-defined alpha spending function as described in the **CTP, section 7.2**.

CTP section 7.3.1. *If the study continues to stage 2, the repeated confidence interval corresponding to the test decision will be calculated, in conjunction with the median unbiased point estimate as estimate for the final adjusted geometric mean ratio. For details see [\(12\)](#).*

Bioequivalence is concluded, if the corresponding (repeated) confidence intervals for the comparison of the primary and secondary endpoints (that did not show bioequivalence in the first stage) are within the pre-specified boundaries 80.00% to 125.00% (original scale).

This step B) may be implemented using function `final.tsd.in` from the R package Power2Stage:

```
final.tsd.in(weight = 0.8, max.comb.test = FALSE,
              GMR1 = GMR1, CV1 = CV1, n1 = n1,
              GMR2 = GMR2, CV2 = CV2, n2 = n2)
```

where GMR1, CV1, n1 are the same values as described above and GMR2, CV2, n2 are the corresponding values obtained from stage 2 data only, i.e. from the proc mixed call in Step 2 A).

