3.3.5 Replacement of subjects

In case more than 4 subjects do not complete stage 1 (of Part B), the Clinical Trial Leader together with the Trial Pharmacokineticist and the Trial Statistician are to decide, if and how many subjects will be replaced. A replacement subject will be assigned a unique trial subject number, and will be assigned to the same treatment as the subject he or she replaces.

Replacing subjects is only allowed, if the total number of exposed subjects will not exceed 72.

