Proprietary confidential information © 2021 Boehringer Ingelheim International GmbH or one or more of its affiliated companies

futility criterion with respect to the confidence interval of the gMean ratio after stage 1, in contrast to the proposed algorithm in [R19-3175]. Otherwise a sample size re-estimation (SSR) based on the unblinded data from the first stage will be performed and the trial continues to stage 2 (Part B).

The SSR will be based on the conditional power as described in [R19-3175], i.e. it will use the conditional error rates as well as the estimated conditional target power for the second stage. For the SSR it is planned to use the observed variability (gCV) and the observed geometric mean ratio (GMR) from the (unblinded) stage 1 data. The overall target power to declare bioequivalence at the end of the trial is planned to be 90%. Note that a specific power adjustment due to multiple endpoints will not be done [R17-0365] and the sample size recalculation, if required, will be based on observed results from primary and secondary PK parameters. The calculation will be performed for each parameter and the highest sample size will be used. Note that the minimum sample size for stage 2 is set to 4, as done and recommended in [R19-3175]. Moreover, for this study a maximum overall sample size of 72 will be considered. Therefore, the number of subjects in stage 2 will not exceed 42, even if the calculated sample size based on stage 1 data is higher than 42.

If bioequivalence is shown for one endpoint but not the other(s), only the endpoint(s) where bioequivalence has not been shown will be tested a second time at the end of the trial [R17-1639]. Note, however, that for completeness all PK parameters and corresponding confidence intervals for the comparison(s) as described in Section 7.3.1 and Section 7.3.2 will be calculated.

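### SAP 7.4.1 caps Part B at 60 counted from the stage-1 PKS, so a dosed subject lost from the PKS lifts the stage-2 ceiling above the protocol's 42

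*SAP*

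**What the plan says.** Protocol 7.4 sets two limits. For the whole trial, "for this study a maximum overall sample size of 72 will be considered". For stage 2 it adds a direct limit: "the number of subjects in stage 2 will not exceed 42, even if the calculated sample size based on stage 1 data is higher". Protocol 3.3.5 repeats the 72 as a limit on exposure: "Replacing subjects is only allowed, if the total number of exposed subjects will not exceed 72".

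SAP 7.4.1 limits a sum instead. It states that "for this study a maximum overall sample size of 60 will be considered", passes "usePE = TRUE, max.n = 60" to the re-estimation function, and explains that "n1 is the number of subjects in the PKS from stage 1". The figure 42 does not appear in that section. SAP section 4 declares all analyses to be in line with the protocol, so no departure is announced.

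The PKS (protocol 7.3, SAP 6.3) keeps any treated subject who contributes a single evaluable primary or secondary PK parameter from a single period.

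**The concern.** The protocol limits n2. The SAP limits n1 + n2, with n1 counted after PKS exclusions. Under a cap on the sum, every subject who leaves the PKS frees one more place in stage 2. The protocol gives no such place back, and the subject who left has already been dosed and counts towards the 72.

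The plan foresees the trigger. Protocol Table 7.2:1 works through stage-1 counts of 17, 16 and 15. SAP Table 6.2:1 lists many deviations that can remove a subject from the PKS. Protocol 3.3.5 considers replacement only when more than four subjects fail to complete stage 1, so a few losses would normally stand. SAP 7.4.1 notes that the weight of 0.8 may be adjusted for such losses, but says nothing similar about max.n.

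The conflict would surface when the trial team holds unblinded stage-1 data and is fixing n2. The additional subjects would be healthy volunteers with no therapeutic benefit (protocol 1.5).

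**Working it through.** **Inputs.** Part A exposed: 12 (protocol synopsis). Stage 1 dosed: 18 (synopsis, 7.4). Stage-2 limit 42 and overall limit 72 (protocol 7.4). SAP cap 60 and n1 = stage-1 PKS count (SAP 7.4.1). Stage-1 alpha 0.03585 one-sided and w = 0.8 × n1*/18 (protocol 7.2). Target power 90% (protocol 7.4).

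**Step 1: reproduce the plan's figure.**
- Protocol: 72 − 12 − 18 = 42.
- SAP with no loss: 60 − 18 = 42.

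The rules coincide at n1 = 18. The SAP's 60 is simply the protocol's 72 without Part A.

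**Step 2: apply the SAP rule after losses from the PKS.** SAP ceiling = 60 − n1. Exposed = 12 + 18 + (60 − n1), taking all 18 as dosed and none replaced.

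| Stage-1 PKS count | SAP ceiling for n2 | Protocol limit for n2 | Exposed under SAP ceiling |
|---|---|---|---|
| 18 | 42 | 42 | 72 |
| 17 | 43 | 42 | 73 |
| 16 | 44 | 42 | 74 |
| 15 | 45 | 42 | 75 |

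**Step 3: how often the ceiling would matter.** The excess arises only if re-estimation asks for more than 42. This was simulated with the inverse-normal two-stage TOST, conditional-power re-estimation, and the observed gCV and ratio (100,000 trials per scenario).

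The set-up was checked against the protocol first:
- Critical values for n1* = 17, 16, 15 came out as 1.83051, 1.85797 and 1.88381. Table 7.2:1 gives 1.83050, 1.85797 and 1.88381.
- At gCV 15%, ratio 109%, overall power, stage-1 power and average size were 95.5%, 79.5% and 22.3. Table 7.7:1 gives 95.2, 79.0 and 22.4.
- At gCV 20%, ratio 109%, they were 89.6%, 56.5% and 32.1. The table gives 89.2, 56.1 and 32.1.

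Share of all trials with n2 above 42 under the SAP cap, given the loss:

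| PKS count | gCV 15%, ratio 109% | gCV 20%, ratio 109% |
|---|---|---|
| 17 | 7.2% | 26.5% |
| 16 | 8.5% | 28.1% |
| 15 | 10.1% | 30.5% |

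The simulation uses a shifted-t approximation to TOST power and fixes the planned ratio at 109%. It does not reproduce the table's overall power at ratios 104% and 114% (at gCV 15%: 99.5 against 97.3, and 74.6 against 83.0). No breach figures are therefore given for those ratios. Steps 1 and 2 do not depend on the simulation.

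**The case against.** The strongest reply is that the protocol already settles the matter. Its 42 is explicit, it anticipates a re-estimate above 42, and it prescribes truncation there. The SAP builds on protocol section 7 and claims conformity with it, and it offers the R call only as one possible implementation. A team following the protocol would stop at 42. This stands, and it rules out two inferences a reader might draw: that over-exposure is bound to follow, and that truncating at 42 after unblinding would be unplanned.

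A reader might also infer that any stage-1 dropout raises the ceiling. The PKS definition does not support that. Someone who misses period 2 but has one evaluable parameter from period 1 stays in the PKS, so n1 remains 18 and the ceiling remains 42. Only a subject with nothing evaluable in either period lowers n1, and protocol 7.2 expects no such loss. Nor does a lower n1 alone push exposure past 72. With 17 dosed and 17 in the PKS, 12 + 17 + 43 = 72, although stage 2 would still exceed 42.

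Finally, the share of continuing trials that reach the cap is not the chance of a breach. At the planning values with n1 = 18 it is 6.09/18.5, about 33%, and there the two rules agree.

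The reply does not remove the SAP sentence itself. Unlike the R call, the cap of 60 is stated without qualification, and the same section defines n1 as the PKS count.

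**Conclusion.** The point holds as a conflict between the SAP and the protocol. Neither 60 nor 42 is miscalculated, but the SAP attaches its cap to the wrong quantity. Once a dosed stage-1 subject leaves the PKS unreplaced, the SAP permits one stage-2 subject above 42 for each such loss: 43, 44 or 45 at PKS counts of 17, 16 or 15, with 73, 74 or 75 exposed.

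Three conditions must coincide: a complete loss from the PKS, no replacement, and a re-estimated n2 above 42. Given the first two, the third occurs in roughly 7–10% of trials at the planning values and 26–31% at gCV 20%, ratio 109%. The documents give no probability for the loss itself, so no unconditional chance can be stated.

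The conclusion assumes that the SAP's overall maximum means n1 + n2 ≤ 60, with n1 as defined there. If n2 had to be even to balance sequences, which the documents do not state, 43 would become 42 or 44. The protocol limit would still govern, so this should be corrected before the interim analysis. It is not evidence that subjects would certainly be over-exposed.

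**What to change.** In SAP 7.4.1, replace the sentence on the maximum of 60 with a statement that n2 will not exceed 42, and set max.n = n1 + 42 in the call. With no replacements this gives n2 ≤ 42 and at most 12 + 18 + 42 = 72 exposed at every PKS count.

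If stage-1 replacements were dosed, the limit on exposure becomes tighter than 42. With d subjects dosed in stage 1, n2 must also satisfy n2 ≤ 72 − 12 − d = 60 − d. The SAP should therefore say that total exposed, Part A plus Part B including replacements, stays at or below 72.

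The cost is one argument and a short text change. The protocol's limits stay as they are, and the weights, alpha levels and decision rules are not affected.

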Test product	alteplase, TPA-05 (50 mg vial)
dose	0.2 mg/kg body weight
mode of admin.	iv-infusion over 30 min

Proprietary confidential information © 2021 Boehringer Ingelheim International GmbH or one or more of its affiliated companies

Reference product	alteplase, TPA-02 (50 mg vial)
dose	0.2 mg/kg body weight
mode of admin.	iv-infusion over 30 min
Auxiliary medicinal product	Heparin-Natrium-5000-ratiopharm® (unfractionated heparin)
dose	5000 IU
mode of admin.	iv-bolus (5 min prior to start of each alteplase infusion)
Duration of treatment	single dose for each treatment
Statistical methods	
Part A:
 
Only descriptive analyses are performed since the generated PK-data that cannot be used for the confirmatory bioequivalence assessment.
 
Part B:
 
The study design is an adaptive two-stage group-sequential design allowing for unblinded sample size re-estimation after stage 1. The assessment of bioequivalence will be based upon 2-sided repeated confidence intervals (CIs) for the ratios of geometric means (test/reference) for the primary endpoints using an acceptance range of 80.00 to 125.00%. The alpha level for stage 1 is fixed to 0.03585 and a user-defined alpha spending function will be used such that the full level of 0.05 is spent at the final analysis. The final analysis will be performed according to the inverse normal approach.
 
The statistical model for each stage of the trial will be an analysis of variance (ANOVA) on the logarithmic scale including effects for sequence, subjects nested within sequences, period and treatment. p-values will be calculated based on the residual error from the ANOVA and the t-distribution.
 
Descriptive statistics will be calculated for all endpoints.

Proprietary confidential information © 2021 Boehringer Ingelheim International GmbH or one or more of its affiliated companies

FLOW CHART

Trial period	Visit	Day	Planned time (relative to start of infusion [h:min])	Approximate clock time of actual day [h:min]	Event and comment	Safety laboratory	Alteplase Infusion	PK blood (x) / ADA (y)	Biomarkers ⁸	Vital signs (BP, PR)	Questioning for AEs and concomitant therapy ⁶
SCR	1	-21 to -1			Screening (SCR) ¹	A				x	
	2	-1	-12:00	20:00	Admission to site, check of restrictions	x ⁵				x	
		1	-1:30	06:30	Allocation to treatment ²			x ²	x ^{2,8}	x ²	x ²
			-0:15	07:45		B		x,y	x ^{8,9}		
			-0:05	07:55	i.v.-bolus of standard heparin						
			0:00	08:00	Start of alteplase infusion		▲				

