7.3 PLANNED ANALYSES

The analyses for endpoint apply for both study parts Part A and Part B. However, since the data of Part A could not be used for a formal statistical assessment all analyses in Part A are only considered to be descriptive.

The data from Part A will be analyses separately and will not contribute to the bioequivalence assessment.

Analysis sets

Statistical analyses will be based on the following analysis sets:

Part A:

- Treated set - part A (TS-A): The treated set includes all subjects who were randomized and treated with at least one dose of study drug. The treated set will be used for safety analyses.
- Pharmacokinetic parameter analysis set - part A (PKS-A): This set includes all subjects in the treated set - part A (TS-A) who provide at least one PK endpoint that was defined as primary or secondary and was not excluded due to a protocol violation relevant to the evaluation of PK or due to PK non-evaluability (as specified in the following subsection 'Pharmacokinetics'). Thus, a subject will be included in the PKS, even if he/she contributes only one PK parameter value for one period to the statistical assessment. Descriptive and model based analyses of PK parameters will be based on the PKS.

Part B (stage I and II):

- Treated set - part B (TS-B): The treated set includes all subjects who were randomized and treated with at least one dose of study drug. The treated set will be used for safety analyses.
- Pharmacokinetic parameter analysis set - part B(PKS-B): This set includes all subjects in the treated set - part B (TS-B) who provide at least one PK endpoint that was defined as primary or secondary and was not excluded due to a protocol violation relevant to the evaluation of PK or due to PK non-evaluability (as specified in the following subsection 'Pharmacokinetics'). Thus, a subject will be included in the PKS, even if he/she contributes only one PK parameter value for one period to the statistical assessment. Descriptive and model based analyses of PK parameters will be based on the PKS.

Adherence to the protocol will be assessed by the trial team. Important protocol deviation (IPD) categories will be described in the IQRMP, IPDs will be identified no later than in the Report Planning Meeting, and the IPD categories will be updated as needed.

Pharmacokinetics

The pharmacokinetic parameters listed in Section 2 will be calculated according to the relevant BI internal procedures. .

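### The SAP's example `final.tsd.in` call counts one-period PKS subjects as full crossovers; used as printed with such subjects, it takes the type I error above 5%

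*SAP*

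**What the plan says.** - **Governing rule.** The protocol synopsis states that "p-values will be calculated based on the residual error from the ANOVA and the t-distribution". Protocol 7.3.1 fits a separate ANOVA to each stage with all effects fixed, including subject within sequence.
- **Final call.** SAP 7.4.1, Step 2 B, offers code for the combination test: "This step B) may be implemented using function" `final.tsd.in`. The printed arguments are the weight, the combination-test option, and GMR, CV and n for each stage. The sentence after it confirms these inputs: "where GMR1, CV1, n1 are the same values as described above and GMR2, CV2, n2 are the corresponding values" from stage 2.
- **Meaning of n.** At the interim step the SAP says that "n1 is the number of subjects in the PKS from stage 1". Protocol 7.3 says of that set that "a subject will be included in the PKS, even if he/she contributes only one PK parameter value for one period".
- **SE and df.** The interim text says that "df1 and SEM1 are the degrees of freedom and standard error of the difference of LSmeans, respectively", taken from PROC MIXED. Neither printed call has arguments for them. The interim call contains an empty argument (`n1 = n1, ,`), so they may have been lost there. The final call has no such gap, and stage 2 equivalents are not mentioned.
- **Incomplete subjects.** Protocol 3.3.5 considers replacement only "In case more than 4 subjects do not complete stage 1", so up to 4 of 18 may be incomplete.

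**The concern.** In a 2x2 crossover with fixed subject effects, a subject seen in one period uses up his only observation on his own subject effect. He contributes neither to the treatment contrast nor to the residual degrees of freedom. A function given only CV and n has to derive both quantities from n, as though all n subjects had completed both periods. The standard error comes out too small and the degrees of freedom too large, so the p-values are too small.

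The endpoints exposed are those that failed at stage 1 and are retested at the end. Dropout is not the only route. Under Protocol 7.3, a Visit 3 predose value above 5% of Cmax or missing samples at important phases can make data non-evaluable, and Protocol 7.5.2 does not impute parameters that cannot be calculated. The count is the same PKS number for every endpoint. An AUC0-∞ missing in one period therefore has the same effect on that endpoint, which must also pass.

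**Working it through.** **Inputs.** From Protocol 7.2, 7.4 and 7.7: n1 = 18, n2 from 4 to 42, stage 1 alpha 0.03585 one-sided, overall alpha 0.05, w = 0.8, c2 = 1.80107, margin ln(1.25), planning gCV 15% and ratio 109%. One-period subjects count in n1*, so n1* stays 18 and w stays 0.8.

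**Assumption.** The documents do not show the function's internals. Given only CV and n, it is taken to use the balanced full-crossover formula with n − 2 df.

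**Reproducing the plan.** A bivariate normal calculation with correlation √w gives c2 = 1.8011, and 1.8305, 1.8580 and 1.8838 for n1* = 17, 16 and 15, matching the protocol. Simulating the design with re-estimation at gCV 15% and ratio 109% gives 95.6% overall power, 79.2% at stage 1 and average N 22.4. Protocol Table 7.7:1 has 95.2%, 79.0% and 22.4. All nine power cells agree within 1 point.

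**Standard error.** SE = √[(MSE/2)(1/na + 1/nb)], with na and nb the completers per sequence. At gCV 15%, MSE = ln(1 + 0.15²) = 0.02225. As printed, na = nb = 9, so SE = √(0.02225/9) = 0.0497 with 16 df.

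| One-period subjects | Completers | Correct SE | Correct df | Printed SE / correct SE |
|---|---|---|---|---|
| 1 | 9 + 8 | 0.0513 | 15 | 0.970 |
| 2 | 8 + 8 | 0.0527 | 14 | 0.943 |
| 4 | 7 + 7 | 0.0564 | 12 | 0.882 |

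**One stage alone.** With m completers and SE approximated as √(2·MSE/m), the true level of a nominal 0.03585 test is P(t with m − 2 df > t(16 df; 0.96415) × √(m/18)). This is 0.0402, 0.0452 and 0.0573 for 1, 2 and 4 one-period subjects.

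**Overall type I error with fixed n2.** True ratio 125%, gCV 15%, 400,000 trials per case, stage 1 decided on the correct SE and df, non-binding futility ignored. Entries are percent as printed, with the result using the correct SE and df in parentheses. Monte Carlo error is about 0.04 points.

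| One-period subjects | n2 = 8 | n2 = 18 | n2 = 42 |
|---|---|---|---|
| 1 in stage 1 | 5.19 (4.97) | 5.26 (5.04) | 5.22 (5.00) |
| 2 in stage 1 | 5.46 (5.01) | 5.50 (5.05) | 5.48 (5.03) |
| 4 in stage 1 | 6.00 (4.93) | 6.14 (5.03) | 6.09 (5.00) |
| 4 in stage 1 plus 2, 4 or 9 in stage 2 | 6.85 (5.01) | 6.61 (5.03) | 6.54 (5.00) |

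Results at gCV 20% are the same within 0.1 points.

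**With n2 re-estimated as planned.** 300,000 trials per case at gCV 10-25% give, as printed:

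- no one-period subjects: 4.9-5.0%
- stage 1 only: 5.1-5.3% (1 subject), 5.4-5.5% (2), 6.0-6.2% (4)
- same share also in stage 2: 5.2-5.3% (1 of 18), 5.5-5.6% (2 of 18), 6.6-7.6% (4 of 18)

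With the correct SE and df, every case lies at 4.9-5.1%.

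**Side point on the stage 2 limit.** The SAP says that "for this study a maximum overall sample size of 60 will be considered". With a PKS n1 of 17 this allows n2 = 60 − 17 = 43, above the protocol's 42. Counting 12 subjects in Part A and 18 dosed in stage 1, the total would be 12 + 18 + 43 = 73, above 72.

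**The case against.** The strongest reply is that the planned test is already right. The protocol bases p-values on the ANOVA, Step 2 A fits PROC MIXED to stage 2 before Step 2 B, SAP Section 4 declares agreement with the protocol, and the R call is only permitted. This stands: a statistician who computes the p-values from the MIXED fits gets a valid test. But the call is the only code the SAP gives for the stage 2 combination test, and as printed it departs from the protocol's rule.

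One-period subjects may also be rare. Dosing is on two consecutive in-house days, the protocol expects n1* = n1, and a subject with no evaluable parameter leaves the PKS and does no harm. This stands too. One such subject costs 0.2-0.3 points in the fixed-n2 cases, and the figures of 6% and above need four.

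If the futility recommendation were always followed, the error at gCV 15% would be 4.7-5.0% with 1-2 one-period subjects and 5.3-5.7% with 4. At gCV 10% it would be about 3.7%, and at gCV 20% still 5.1-6.5%. Because the rule is non-binding, error control should not rely on it.

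The function's internals are an assumption, though hard to avoid given the inputs listed. On the side point, Protocol 7.4 already caps stage 2 at 42, and 43 cannot be split equally between sequences, so this is only a matter of aligning wording.

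**Conclusion.** The concern holds, conditionally. If the trial reaches stage 2, some PKS subjects contribute one period only, and the call is used as printed, the overall type I error exceeds 5%. The excess is a few tenths of a point with 1 or 2 such subjects in stage 1 and about 1 point with 4. In the re-estimated design it reaches up to 2.6 points (7.6%) if the 4-of-18 share recurs in stage 2. This rests on the function rebuilding SE and df from n, and on non-binding futility being ignored. The stage 1 decision comes from the MIXED confidence interval and is unaffected. In the planning case that decision succeeds 79% of the time, so stage 2 would be needed in at most 21% of trials. It should be corrected because the printed code departs from the protocol's own test and the correction is nearly free.

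**What to change.** For each endpoint, take the standard error of the treatment difference and its degrees of freedom from the stage 1 and stage 2 PROC MIXED fits. Either pass them to `final.tsd.in` as SEM1, df1, SEM2 and df2 (and SEM1 and df1 to `interim.tsd.in` if they are missing there), or compute p1j and p2j directly from the fits. The direct route does not depend on the function's arguments. Error control needs no change to n1*, w or Protocol 7.2.

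Separately, state in the SAP that n2 may not exceed 42, together with the overall limit of 72.

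The cost is an edit to the SAP's example code and one sentence of text, plus a line for the stage 2 limit. No protocol amendment and no extra data are needed.
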